**unRaveling pErioperative
MyocArdial INjury (REMAIN)**

**Department of Anesthesiology
Erasmus MC, Rotterdam, The
Netherlands**

non-WMO-applicable research

Full title of protocol	unRaveling perioperative Myocardial INjury
Short title or Acronym	REMAIN
Version	2
Date	26-09-2024
Coordinating investigator/ project leader	Dr. [name] Erasmus University Medical Center Department of Anesthesiology [name], The Netherlands
Principal investigator(s)	Dr. [name] en Dr. [name]
Sponsor (in Dutch: verrichter/opdrachtgever)	Erasmus MC, University Medical Center Rotterdam Department of Anesthesiology [name] [name], The Netherlands
Subsidising party	N.A.

TABLE OF CONTENTS

List of abbreviations and relevant definitions	4
Protocol summary	5
1. Introduction and rationale	6
2. Objective(s)	6
3. Study type	6
4. Study population	7
5. Methods	7
6. Unexpected discoveries	8
7. Exchange, sharing or transfer of data and/or human material and/or images outside the Erasmus MC	8
8. Statistical analysis	8
9. Recruitment and consent	8
10. Handling and storage of data and images	9
11. Handling and storage of human material	9
12. Amendments	10
13. Publication	10
14. References	10
15. Attachments	10

LIST OF ABBREVIATIONS AND RELEVANT DEFINITIONS

DRE	Digital Research Environment
Exception consent	Form Care for data Template, in Dutch: Formulier uitzondering toestemming
GCP	Good Clinical Practice
IC	Informed Consent
KLEP	Klinische Epidemiologie
UAVG	Dutch Act on Implementation of the General Data Protection Regulation; in Dutch: Uitvoeringswet Algemene Verordening Gegevensbescherming
WMO	Medical Research Involving Human Subjects Act, in Dutch: Wet Medisch- wetenschappelijk Onderzoek met Mensen

SUMMARY

Rationale: Myocardial injury is an independent predictor for poor outcome after non-cardiac surgery. The causes for myocardial injury can be multifactorial. Knowing what the exact cause for myocardial injury is, is often unclear or mixed pathophysiology exist. However, in clinical practice doctors have an opinion on the most likely cause.

Objective: The aim of this study is to gain insight into the etiology of myocardial injury after non cardiac surgery. Secondary we try to find what doctors think of the most logical explanation for myocardial injury, what phenotype is associated with the most likely cause, how this determines prognosis and what factors are associated with improved outcome.

Study design: Retrospective cohort study

Study population: Patients who underwent non-cardiac surgery in the Erasmus MC in the period 2017-2023.

Intervention: None

Main study parameters/endpoints: The primary endpoint is a description of the main etiologies found within patients with an elevated troponin T after non cardiac surgery.

Nature and extent of burden and risks associated with participation, benefit and group relatedness:

There will not be a significant burden to patients. This study will use existing data from patients that have been operated in the time period 2017-2023 in the Erasmus MC. There is no additional intervention required.

1. Introduction and rationale

Myocardial injury, a significant increase/or elevation of cardiac troponin after non-cardiac surgery, has proven to be a major contributor to perioperative mortality[1, 2]. It is estimated that myocardial injury contributes to 34-42% of all deaths following non-cardiac surgery within 30 days [3]. One major difference between non-surgical acute myocardial infarction and perioperative myocardial injury is that the vast majority of patients experiencing perioperative myocardial injury do not show any typical ischemic symptoms (chest pain and/or ischemic changes on the electrocardiogram). It is therefore difficult to diagnose myocardial injury, without knowing biomarker profiles. Due to the lack of typical symptoms, most patients with myocardial injury are currently not detected in routine clinical practice. Surprisingly, whether a patient fulfills the definition for acute myocardial infarction (i.e. has clinical symptoms, or ECG changes, or imaging evidence of new loss of viable myocardium), the prognosis is the same for all elevations, regardless of symptoms [3-5].

In the last decade, extensive efforts have been made to determine the etiology of myocardial injury, in order to discover a pathophysiology that is leading and may guide us to treatment options. One of the published definition is MINS (Myocardial Injury after Noncardiac Surgery) [4, 6-8]. This definition evaluates all elevations for any other cause that may be causing the elevation (i.e. sepsis, heart failure, tachyarrhythmias, renal failure, chronic elevations). If any of these other causes are unlikely, a diagnosis of MINS can be made; MINS therefore covers the spectrum of ischemic heart disease (acute coronary syndromes and type 2 ischemia). Unfortunately, it is not known which criteria are used to rule out other causes, the individual contribution on mortality of the other phenotypes or how often mixed etiologies are possible.

A second strategy has recently been published by another research group (Figure 1) [9]. Here an increase in troponin in the first steps is analyzed for a cause other than type 2 ischemia. If there is, treatment may be started appropriate to the most likely cause. Thus, by definition, if no other cause found likely, type 2 ischemia becomes the most logical cause. The prognosis varies greatly depending on what researchers found the most likely cause [9, 10]. These results call for an replication in our hospital, since we have been measuring myocardial injury for more than a decade. Furthermore, it is unclear anesthesiologists in different phases of training, agree with regard to the most likely cause of the myocardial injury. In this study we would like to search for more clarity regarding these questions, which are better elaborated below.

[figure not shown]

Figure 1: Evaluating scheme for patients with perioperative myocardial injury

2. Objective(s)

The aim of this study is multiple:

Primary aim:

- The primary aim is to determine the etiology of myocardial injury after non cardiac surgery.

Secondary aims:

- Do phenotypes, with regard to blood pressure, heart rate, of ST-segment analysis, differ between the different etiologies?
- How often do health care providers from different levels of training differ in opinion on the most likely diagnosis?
- What were clinical features present for selecting the most likely etiology?

3. Study type

3.1 *Study type:*

Retrospective
 Prospective
 Combination Retrospective/Prospective

3.2 Check all the applicable boxes:

Medical records (re-use of data from healthcare, including AI) Case report
 Re-use data from research
 Evaluations of quality of healthcare (retrospective)
 Research with additional use of residual material from regular healthcare
 Research with re-use of human materials from research or existing biobank
 Research with human materials without biobank
 De novo biobank (human material obtained without burdensome or invasive procedures)
 Post marketing survey research with medical devices
 Phase IV research
 Healthcare evaluation research (prospective) Medical devices
 In Vitro Diagnostic Tests Other research, describe

4. Study population

4.1 *Population (base)*

The population to be studied consists of all non-cardiac surgical patients who underwent surgery at Erasmus MC in the period 2017-2023.

4.2 *Inclusion criteria*

In order to be eligible to participate in this study, a subject must meet all of the following criteria:

- Age > 18 year of age
- Undergoing non-cardiac surgery in the Erasmus MC, with (high-sensitive) Troponin T > 50 ng/L measured in any of the first three days after surgery.

4.3 *Exclusion criteria*

The following types of operations are excluded from the analysis:

- Re-operations within the study period.
- Daycare surgery

4.4 *Sample size calculation*

The sample size is based on convenience sampling of the cohort of routine postoperative troponin measurements in the Erasmus MC since 2017 (MEC-2017-062). A total of 100 patients per year with a (high-sensitive) Troponin T > 50 ng/L are estimated [11] which would result in roughly 700 patients.

4.5 *(Planned) start date*

Baseline and in hospital data extraction can be started as soon as approval by the ethics committee is given. We plan to start as soon as we receive permission to collect the necessary data. Expected start date is October 2023.

4.6 *(Planned) end data*

March 1st 2027

5. Methods

5.1 *Procedures*

The baseline population will consist of all patients who underwent a form of non-cardiac surgery, regardless of the type of anesthesia in the time period 2017-2023 in the Erasmus MC. For patients who have undergone multiple operations, only the first operation will be included for analysis. There are no restrictions to the type of anesthesia: local, locoregional and general

anesthesia will be included. The same applies for the type of surgery: emergency as well as elective surgery will be included. Baseline variables, medication use, type of surgery and perioperative hemodynamic and laboratory variables will be extracted from the hospital information system. Myocardial injury will be defined as a peak high-sensitive troponin T > 50 ng/L, measured on one of the first three postoperative days. One year mortality is registered, as well as major vascular events. This is in line with previous publications from our group. The adjudication strategy used for patients with myocardial injury will follow a similar pattern compared to scheme in Figure 1. For the adjudication process anesthesiologists in various forms of training (resident and attending) will be invited. The total panel will have a maximum of 6-10 members. Two members will receive a sample of patients to adjudicate. Together the entire panel will adjudicate all patients. In case of non-agreement between raters, a third rater will make a final decision. The goal to investigate the differences between the raters.

5.2 *Standard clinical care versus extra for research*

N.A.

5.3 *Please describe the burden and risks associated with participation, e.g. the amount and number of blood samples, biopsies, liquor, hair, urine, nails, saliva etc., the number of site visits, physical examinations or other tests, questionnaires or diaries that have to be filled out, physical and psychological discomfort associated with participation*

N.A.

5.4 *A risk-benefit analysis must be given, if applicable.*

N.A.

5.5 *Medical device(s)/In vitro diagnostic tests*

N.A.

6. Unexpected discoveries

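### Section 5.1 makes no provision to mask etiology raters to later outcomes, and aim 1 may compare variables that helped to choose the labels

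*Protocol*

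**What the plan says.** **How the label arises.** The Protocol Summary says: "This study will use existing data from patients that have been operated in the time period 2017-2023 in the Erasmus MC". Section 5.1 says: "The adjudication strategy used for patients with myocardial injury will follow a similar pattern compared to scheme in Figure 1". It then says: "Two members will receive a sample of patients to adjudicate", with a third rater deciding when two disagree. It does not list what a rater is given for each patient.

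**What is compared across the label.** The first secondary aim in section 2 reads: "Do phenotypes, with regard to blood pressure, heart rate, of ST-segment analysis, differ between the different etiologies". The third reads: "What were clinical features present for selecting the most likely etiology". Section 5.1 adds that "perioperative hemodynamic and laboratory variables will be extracted from the hospital information system".

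**Outcomes.** Section 5.1: "One year mortality is registered, as well as major vascular events". The Summary objective includes how the presumed cause relates to prognosis. The Introduction reports that prognosis differed strongly by adjudicated cause in earlier work and calls for those results to be replicated locally. The aims in section 2 and the endpoints in section 8 do not list this question.

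**Access to data.** Section 10.1 places baseline, outcome, hemodynamic and laboratory data in the same research environment and anonymizes them only once adjudication is finished. Section 10.2 limits access to staff involved in data management and analysis. Neither section mentions masking of raters.

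**The concern.** Etiology here is a judgment made after the event, not a measurement. A comparison across such labels can be trusted only as far as the compared quantity was kept out of the judgment. Two comparisons are exposed.

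The first is prognosis by cause. A rater who knows that a patient died within the year, or later had a vascular event, may lean toward a cause regarded as dangerous. The labels would then carry outcome information, and the gradient that the protocol hopes to replicate would be partly self-made. Once the labels exist, no analysis can remove that information. Repair would need re-adjudication by new, masked raters.

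The second is aim 1. If a rater used heart rate, blood pressure or ST-segment findings to choose the label, a difference in that variable between labels partly shows how raters decide. Read as evidence of distinct phenotypes, it would be circular.

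**Working it through.** **The plan's own figure.** Section 4.4 expects 100 patients a year over 2017 to 2023, which is 7 calendar years: 100 × 7 = 700. This reproduces. The concern rests on no other figure in the protocol, and the fix does not change this one.

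**Step 1: is there a masking provision?**
- Section 5.1 describes panel, pairing and tie-break, but neither the content of the case file nor masking.
- Section 10.1 anonymizes after adjudication, so that step cannot mask the raters.
- Section 10.2 restricts access in general terms. It does not say whether raters count as study staff, or whether they open the patient chart.

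The protocol is therefore silent: it neither withholds outcomes from raters nor says that raters see them.

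**Step 2: does outcome by label matter to this study?** The Summary and the Introduction say so; sections 2 and 8 do not list it. Section 9.3 names 1-year mortality as the primary endpoint, which conflicts with section 8.1. That conflict is a separate matter and does not show that mortality by etiology will be analysed.

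**Step 3: how large could outcome leakage be?** All inputs here are assumptions: two labels A and B, equally frequent apart from leakage, with equal true risk; 20% one-year mortality; a share q of all labels (survivors included) set by vital status as the rater knows it; a share v of deaths visible to the rater.

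- P(A | alive) = (1 − q)/2
- P(A | dead) = (1 − q)/2 + v·q
- Odds ratio = odds of A among the dead ÷ odds of A among the living. It does not depend on the mortality rate.

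For q = 0.10 and v = 1: P(A | alive) = 0.45 and P(A | dead) = 0.55, so the odds ratio is (0.55/0.45) ÷ (0.45/0.55) = 1.49. At 20% mortality, label A has 0.11/0.47 = 23.4% deaths and label B 0.09/0.53 = 17.0%.

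| Share of deaths visible (v), q = 0.10 | P(A given dead) | Odds ratio |
|---|---|---|
| 1 | 0.55 | 1.49 |
| 0.5 | 0.50 | 1.22 |
| 0.3 | 0.48 | 1.13 |
| 0.1 | 0.46 | 1.04 |
| 0 | 0.45 | 1.00 |

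With all deaths visible, q = 0.05 gives 1.22 and q = 0.25 gives 2.78.

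**Step 4: a second model as a check.** Assume a label given to 30% of survivors and x points more often to those who died, again with 20% mortality.
- x = 5 points: risk ratio = (0.07/0.31) ÷ (0.13/0.69) = 1.20.
- x = 10 points: risk ratio = (0.08/0.32) ÷ (0.12/0.68) = 1.42.

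Both models give a ratio of 1.0 when raters cannot see the outcome.

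**Step 5: aim 1.** Aim 3 expects clinical features to select the label, and aim 1 compares clinical variables between labels. Nothing separates the two sets. A variable used for labelling will differ between labels partly by construction. How much cannot be calculated, because Figure 1 is not shown and the text does not itemize the study's own labelling criteria.

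**The case against.** **Silence is not exposure.** A reader might infer from section 5.1 that raters will be shown one-year mortality. The text does not say so, and section 10.2 restricts access, although only in general terms. This objection stands, and the point is limited to the absence of a provision.

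**The labelling inputs are unseen.** A reader might also infer that heart rate, blood pressure and ST-segment are all inputs to the label. The documents do not show this for any of the three. The Introduction lists "sepsis, heart failure, tachyarrhythmias, renal failure, chronic elevations" as competing causes and mentions ECG changes, but those belong to other definitions, not to this study's scheme. It adds that most of these patients show no typical ischemic symptoms, counting ECG changes among these, which would limit how often ST could decide a label. This also stands. Further, if tachyarrhythmia is one of the causes, a heart rate difference is partly real, so it would be wrong to treat every such difference as spurious.

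**Aim 1 may be meant as description.** The Summary presents the labels as doctors' opinions, and no test or causal claim is stated. Reporting aim 1 as descriptive can be settled after adjudication. That is fair, but limiting inference to variables not used in labelling requires a record of the deciding features, which must be made during adjudication.

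**Prognosis is not a listed aim.** True for sections 2 and 8. The Summary and the call for replication still make the comparison likely enough to protect, and masking cannot be added to labels already given.

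**Conclusion.** The point holds as a cheap improvement to section 5.1. The protocol has etiology assigned retrospectively, registers later deaths and vascular events, wants prognosis compared by assigned cause, and makes no provision to mask raters.

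The possible size depends on assumptions that the protocol cannot settle. With 10% of labels following vital status, the spurious odds ratio ranges from 1.49 if every death is visible to 1.04 if one in ten is. These are illustrations, not estimates for this study, and there is no bias if raters never see outcomes.

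For aim 1 the circularity holds in principle for any variable used in labelling. Which of the three variables that covers is unverified, so no size is claimed. The primary description of assigned etiologies and the rater-agreement aim are not affected by the aim 1 circularity.

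**What to change.** - **Section 5.1, case file.** State what raters receive, and leave out vital status and vascular events after a stated adjudication window. Counting the window from the three-day troponin period rather than from discharge would also hide later in-hospital deaths where feasible. The third rater should work from the same file.
- **Section 5.1, adjudication form.** Add a short field in which each rater marks the features that decided the label. Aim 3 needs this anyway.
- **Sections 2 and 8.2.** Report aim 1 as a description of the assigned labels, and limit any inferential claim of distinct phenotypes to variables not used in labelling.

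**Cost.** Wording in three sections, one form field and the preparation of masked files. The expected 700 patients and the endpoints do not change. The downsides are less late diagnostic information for raters and a weaker aim 1 claim.

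**Timing.** The expected start was October 2023, this version is dated September 2024 and the planned end is March 2027, so adjudication may already be under way. Labels already given without masking should be reported as unmasked, or a subset re-adjudicated by new, masked raters.

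### Injury after surgery is defined by one absolute troponin level with no change required, so stable or pre-existing elevation enters the etiology denominator and can default to type 2 ischemia

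*Protocol*

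**What the plan says.** **Entry and definition.** Section 4.2 admits adults having non-cardiac surgery "with (high-sensitive) Troponin T > 50 ng/L measured in any of the first three days after surgery". Section 5.1 makes the same level the definition: "Myocardial injury will be defined as a peak high-sensitive troponin T > 50 ng/L, measured on one of the first three postoperative days". Neither section requires a preoperative value, a rise, or a rise or fall across the three days.

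**Exclusions.** Section 4.3 opens with "The following types of operations are excluded from the analysis" and lists only re-operations and daycare surgery. Section 5.1 adds that "emergency as well as elective surgery will be included".

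**Source of the values.** Section 4.4 describes "convenience sampling of the cohort of routine postoperative troponin measurements in the Erasmus MC since 2017". No preoperative sampling is mentioned, although section 5.1 does plan to extract perioperative laboratory results from the hospital system.

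**The scheme to be followed.** Section 1 says of the published strategy: "Here an increase in troponin in the first steps is analyzed for a cause other than type 2 ischemia". If no other cause is judged likely, type 2 ischemia is the answer. The authors then write "These results call for an replication in our hospital", and section 5.1 commits adjudication to a pattern similar to Figure 1.

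**Chronic elevation.** In section 1, under the MINS definition, the protocol names rival explanations: "i.e. sepsis, heart failure, tachyarrhythmias, renal failure, chronic elevations". The text gives no rule for handling them in this study.

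**The concern.** The primary aim in section 2 concerns injury that arises after surgery. A single level cannot show when troponin rose. Consider an elective patient with renal failure and a steady 60 ng/L, and an emergency patient already above 50 ng/L before incision. Both meet the definition, although surgery may have caused no injury in either. Each is then put to a panel that must choose the most likely cause.

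Two things are at stake:

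- **The type 2 share.** Type 2 ischemia is what remains when nothing else seems likely. A stable elevation with no evident acute cause can fall there, so any error has a likely direction, and a larger sample would not remove it.
- **The comparison with the published results.** This cohort enters on a level, while the scheme is described as starting from an increase. A difference in etiology shares could come from entry alone. The blood pressure, heart rate and ST-segment comparisons in the first secondary aim could likewise include patients without an acute event.

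**Working it through.** **The plan's own figure.** Section 4.4 expects 100 patients per year. Over 2017 to 2023 (7 calendar years) that gives 100 × 7 = 700, which matches the stated figure. It counts patients above 50 ng/L, not patients with a demonstrated change.

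**Inputs for the illustration.** Neither input is in the documents; both are assumptions.

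- c = share of entrants with stable or pre-existing elevation
- t = true share of type 2 ischemia among acute injuries

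**Formula.** If all of share c fall to the residual class, the reported type 2 share is t(1 − c) + c = t + c(1 − t), and the shift is c(1 − t).

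**With t = 50%:**

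- c = 10%: 0.50 + 0.10 × 0.50 = 55%
- c = 25%: 0.50 + 0.25 × 0.50 = 62.5%

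**Wider range:**

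| c | Patients of 700 | Remaining | Reported share if t = 40% | Reported share if t = 60% |
|---|---|---|---|---|
| 5% | 35 | 665 | 43% | 62% |
| 10% | 70 | 630 | 46% | 64% |
| 20% | 140 | 560 | 52% | 68% |
| 30% | 210 | 490 | 58% | 72% |
| 40% | 280 | 420 | 64% | 76% |

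**Against sampling error.** The 95% half-width at n = 700 and a 50% share is 1.96 × √(0.5 × 0.5 / 700) = 3.7 points. With t = 50%, the shift c × 0.5 exceeds this once c passes 0.037 / 0.5 = 7.4%.

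**The other extreme.** If none of these patients is labelled type 2 ischemia, its share of the whole cohort is t(1 − c): 0.50 × 0.90 = 45% at c = 10%, and 0.50 × 0.75 = 37.5% at c = 25%. These could be correct shares of all patients with elevated troponin, but they are still not shares of acute injury. The all-or-none cases are bounds, not forecasts.

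**The case against.** The strongest reply is that Figure 1 decides the matter and cannot be seen here. It may contain a branch for chronic elevation or a step that looks at change, and the scheme's first steps do search for causes other than type 2 ischemia. This stands as a limit. A reader might infer that these patients are certain to be given a perioperative cause; the documents support only that they can be. What survives is the definition itself, which counts a stable value above 50 ng/L as injury after surgery whatever the figure shows.

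Second, a reader might infer that change in troponin will not be recorded. The text does not support that. Perioperative laboratory results are extracted, and a peak implies that repeat values are considered where they exist. The gap is that no stated rule uses them.

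Third, section 8.1 describes etiologies among patients with elevated, not risen, troponin. For that denominator a chronic cause is a legitimate answer, so it would be too strong to say that every etiology share is biased. The endpoint is nevertheless meant to serve an aim about injury after surgery, and the two populations differ.

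Fourth, section 1 uses increase and elevation almost interchangeably, and the protocol promises only a similar adjudication pattern, not identical entry criteria. The mismatch with the scheme therefore rests on the protocol's own short description and is not a formal contradiction. Section 5.1 also appeals to consistency with the group's earlier work, so the threshold may be deliberate. That does not show that a level alone suits the attribution of cause.

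Finally, the numerical delta can reasonably be left to an analysis plan or adjudication manual. The definition of injury and the basis for adjudication are fixed in this protocol.

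**Conclusion.** The point holds in a limited form. Sections 4.2 and 5.1 define injury after surgery by one absolute level, require no change, and exclude neither chronic nor pre-existing elevation. Such patients enter the denominator and can be assigned a perioperative cause, by default type 2 ischemia, unless the Figure 1 scheme separates them.

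The size of the effect cannot be derived from the documents. The 5 points at t = 50% and c = 10% rest on two assumed inputs and on every such patient falling to the residual class. If Figure 1 already provides a chronic category and adjudicators use it, the distortion of the type 2 share among acute injuries is avoidable by reporting within the acute cases. A stated rule for recognising chronic elevation would still be needed. This is a worthwhile, inexpensive improvement and does not invalidate the study.

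**What to change.** Keep the > 50 ng/L cohort and its expected 700 patients.

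1. **Section 5.1, before adjudication.** From troponin values already in the record, place each patient in one of three groups: acute change shown (against any preoperative value, or across days 1 to 3, by a pre-set delta); stable or pre-existing elevation; not assessable.
2. **Adjudication.** Confirm that chronic or pre-existing elevation is an available outcome, and add it if Figure 1 does not already provide it.
3. **Section 8.1.** Report the etiology distribution overall and within the acute-change group, use the latter for comparison with the published results, and state how many patients are not assessable.

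**Cost.** Some protocol wording and one derived variable from laboratory data already planned for extraction. The acute-change group will be smaller than 700 and selected by who had repeat or preoperative measurements, so its percentages are less precise. For example, 630 patients at a 50% share give a half-width of 1.96 × √(0.25 / 630) = 3.9 points against 3.7 at 700, before any loss to the not-assessable group. That group could be large, because the cohort rests on routine postoperative sampling.
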